Separate evaluations for third line use of axitinib following prior therapy with sunitinib in the first line followed by e.g. nivolumab, cabozantinib, or lenvatinib/everolimus in the second line are urgently needed. The efficacy of axitinib can continue to be documented after directly preceding therapy with sunitinib. These investigations allow a comparison of the efficacy and tolerability of axitinib in different lines.

Therefore, the following information is of particular interest during the course of the investigation:

- Efficacy (maximum response, survival time, progression-free time)
- Treatment tolerability (assessment by physician)
- Safety profile (overall incidence of adverse events and rate of side effects) of patients with advanced RCC, r/rMCL and GIST receiving treatment with temsirolimus, sunitinib, or axitinib
- Profile, comorbidities and characteristics of patients receiving treatment with temsirolimus, sunitinib, or axitinib
- The sequence of systemic therapies for advanced RCC, MCL, and GIST
- Patient interview on quality of life in advanced RCC patients

Temporal sequence

The following time points were defined as the minimum period for the implementation of the registry:

- Patient Recruitment Phase: January 2008 December 2020
- Recruitment rate: 100 patients/year per product
- Average observation period per patient: 6 months for temsirolimus, 12 months for sunitinib, 6 months for axitinib
- Field Phase: December 2021
- Total duration: 14 years + 1 year evaluation and report (2022)

Since the goal is to keep patients in the registry for life, the registry can be continued indefinitely.

The end of data collection is scheduled for December 2021.

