11. METHODOLOGY

The registry is designed to document the disease progression in patients with advanced renal cell carcinoma, relapsed/refractory mantle cell lymphoma, and gastrointestinal stromal tumor intended by the treating physician for systemic therapy.

During the course of the registry, the following (minimum) number of survey times and endpoints are planned:

At observation start: Enrollment Visit

During the course of the observation: Follow-up documentation (as per local guidelines, generally every

8 - 12 weeks)

End of observation: Completion/Discontinuation Form

1-year follow-up for subjects who discontinue therapy: Survival form (every 6 months thereafter)

[figure not shown]
The temporal sequence and number of follow-up documentation items depends on medical practice to perform confirmatory imaging procedures and patient survival.

The completion of the continuous observation documentation (follow-up visits) takes place with the completion or discontinuation of the case report form below:

- Patient death.
- Patient lost to follow up due to patient request/withdrawal of patient informed consent,
- Change in therapy or discontinuation due to intolerance to temsirolimus, sunitinib, and axitinib or progression.

For the indication **metastatic renal cell carcinoma**, prospective documentation of sequential therapy is an option. According to the approvals of temsirolimus, sunitinib and axitinib, e.g. the following therapy sequences are possible:

• Sunitinib (as first-line therapy) followed by axitinib

- Temsirolimus (as first-line therapy) followed by sunitinib
- Axitinib (as second-line therapy, 1st Pfizer therapy sequence) followed by sunitinib
- Sunitinib (as first-line therapy) followed by a second-line approved active substance (interim documentation) followed by axitinib (in the third line or a later line)

Herein two consecutive Pfizer lines of therapy or two Pfizer lines of therapy with one or more intermediate therapies can be documented. The following documentation sheets are available for this purpose:

White documentation section: 1. Pfizer Therapy sequenze, e.g. Sunitinib

- Enrollment Visit
- Follow-up documentation every 8-12 weeks
- Final Assessment/Discontinuation of documentation

Pink Documentation section. Interim documentation for non-Pfizer products, e.g. nivolumab

• Every 8-12 weeks

Green documentation section. 1. Pfizer Therapy Sequence

- Initial visit to change treatment
- Follow-up documentation every 8-12 weeks

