The following is a schematic of all parameters to be recorded as part of this registry (imaging examination results if available).

Flow chart for the registry course for GIST and MCL

	Enrollment visit	Follow-up visit (every 8-12 weeks)	Completion Exam/ Discontinuation	Survival sheet (12 months after completion/ discontinuation)
Demographic data	X	X	X	Х
Inclusion/exclusion criteria	X			
Patient Informed Consent	X			
Tumor history	X			
Karnofsky Performance	X	X		
Treatment/Medication				
Pretreatment	X			
Concomitant medication	X			
Tumortherapy	X	X		Х
Safety				
Concomitant diseases/physical	X			
Lab values	X	X		
Electrocardiogram	X	X		
Documentation of adverse events		X	X	
Efficacy				
Subjective prognostic assessment by	X			
CT/MRI scan	X	X		
Ultra sound	X	X		
Chest X-ray	X	X		
Assessment of response to therapy by		X		
Therapy assessment of efficacy and tolerability		X		
Physician's overall assessment of therapy response			X	

Flow chart of mRCC sequence documentation:

	1 0 1		Interim documentation for non-Pfizer products	2. P	fizer Therapy Seq	SurvivalSheets		
	Enrollment Visit	Follow-up visit every 8-12 weeks	Completion/ Discontinuation of Documentation	Interim documentation every 8-12 weeks	Initial visit to change treatment	Follow-up visit every 8-12 weeks	Completion/ Discontinuation of Documentation	Survival Sheet 12 months after discontinuation, then every 6 months
Demographic data	X	X	X		X	X	X	X
Inclusion/exclusion criteria	X							
Patient Informed Consent	X			(x)				
Tumorhistory	X				X			
Karnofsky Performance Status/Height/Weight	X	X			X	X		
Treatment/ Medication								
Pretreatment	X							
Concomitant medication	X				X			
Tumor therapy	X	X		X	X	X		X
Safety								
Concomitant disease(s)/physical exam	X				X			

Labvalues	X	X			X	X		
Blood pressure	X	X			X	X		
Electrocardiogram	X	X			X	X		
Echocardiogram	X	X			X	X		
Pa in a ssessment	X	X			X	X		
Documentation of adverse events		X	X	X	X	X	X	
Efficacy		•				•		
Subjective prognosis assessment by the physician	X				X			
CT/MRI scan	X	X				X		
Ultra sound	X	X				X		
Chest X-ray	X	X				X		
Tumor Assessment		X		Х		X		
Physician's assessment of efficacy and tolera bility of the therapy		X				X		
Global assessment of therapy response by the physician			X	х			X	

Patient Quality of Life Survey	X	X			X	X		
-----------------------------------	---	---	--	--	---	---	--	--

Biometric evaluation

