In case an event (either death or progression) was present and date of event was documented, the following definitions was used:

Overall Survival (OS, months) = $\frac{\text{date of death} - \text{date of baseline visit} +1}{365.25 *12}$

Progression Free Survival (PFS, months) = (minimum of (date of death, date of progression) – date of baseline visit + 1)/365.25 * 12.

In case information on dates were partly or completely missing or contradictory, the following was done:

• PFS:

- o the presence of a progression was confirmed, but no date was documented: if date of last intake of study medication was given, this date was used as date of progression, otherwise the date of the last visit with a documented "non-progression (e.g. SD)" was used as date of progression.
- o the presence of a progression was confirmed, but dates within a visit and on final documentation were contradictory, the prior date was used.
- o in case a death was documented within a survival follow-up/ within sequence 2 for subjects from sequence 1, but no progression was documented within regular study, the date of last visit + 1 day was used as date of progression.
- o in case no progression was documented, subject was censored with the latest available contact date / assessment date within study/within sequence.
- o in case these rules led to a missing duration or a negative duration, duration was set to "1 day".

• OS:

- o in case a death was documented, but date of death was unknown, the date of death was substituted with the latest available date for the patient (last visit, last contact date, date of assessment)
- o in case no death was documented, subject was censored with the latest available contact date / assessment date within study.
- o in case these rules led to a missing duration or a negative duration, duration was set to maximum of (PFS,"1 day").

Response to therapy (Recist criteria/ Cheson criteria)

Response to therapy according to the Recist/ Cheson criteria will be analyzed using the physician's assessment as documented in the CRF. As neither "size of lesion", "new lesions" or "increase in size" are defined as key fields, contradictory answers will not overvote physicians assessment.

"Best response" will be analyzed using the physician's assessment at final visit. If "Best response" is missing it will be determined from the best response documented during previous follow-up visits.

Treatment

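### Best response follows the final-form entry with no rule for disagreement with the visits, so the analysed maximum can differ from the best visit assessment

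*SAP*

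**What the plan says.** The protocol's list of information of particular interest (section 6) begins with "Efficacy (maximum response, survival time, progression-free time". Protocol section 11, under the analysis of efficacy criteria, lists maximum response separately from the physician's assessment of response.

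SAP Appendix 1, A1.3 turns this into a derivation. Best response "will be analyzed using the physician's assessment at final visit". If that item "is missing it will be determined from the best response documented during previous follow-up visits". These two sentences are the whole rule.

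A1.3 contains two other rules on conflicting data:

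- **Lesion fields against the physician's rating:** "contradictory answers will not overvote physicians assessment".
- **Progression recorded differently at a visit and on the final form:** progression is confirmed, "but dates within a visit and on final documentation were contradictory, the prior date was used".

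In the protocol flow charts, the response item on the completion form is called "Global assessment of therapy response by the physician" for mRCC and "Physician's overall assessment of therapy response" for GIST and MCL. The tumour or response assessment made at each visit is a separate row and is not marked at completion. The SAP flow chart has the same layout.

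**The concern.** A maximum over the course of therapy cannot be lower than a value documented during that course. The A1.3 rule allows this, because a completed final entry is taken as it stands and the visit assessments play no part. Disagreement between the two sources is foreseeable. The final form is a summary written at the end, and one listed reason for ending the documentation is "Change in therapy or discontinuation due to intolerance to temsirolimus, sunitinib, and axitinib or progression". The SAP foresaw a conflict between visits and final form for progression dates but has no counterpart for response.

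At stake is a named efficacy endpoint. Table 2.1-2 reports it for every indication, in total and by risk group. The same table splits it into confirmed and not confirmed (except for temsirolimus in MCL), and the SAP does not say how that split is derived. If a final-form CR or PR matches no visit, there is no visit date on which to base its confirmation.

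**Working it through.** The plan has no figure of its own to reproduce here. The check is a trace of the A1.3 rule.

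**Inputs.** The final entry takes precedence if present, and visits are used only if it is missing (SAP A1.3). The target is the maximum response (Protocol sections 6 and 11).

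| Case | Visit assessments | Final form | Result under A1.3 | Best over visits |
|---|---|---|---|---|
| a | PR, PR, PD | PR | PR | PR |
| b | PR, PR, PD | PD | PD | PR |
| c | PR, PR, PD | blank | PR | PR |
| d | SD, SD | PR | PR | SD |

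- Case a is the ordinary one, and nothing is lost.
- Cases b and c have identical visits but different endpoints. The only difference is whether the final field was completed.
- Case d errs in the opposite direction if the final entry is wrong. It is correct if the response was first seen after the last visit.
- The lesion rule does not help in b or d. It ranks lesion data below the physician's rating, whereas here two ratings by the physician disagree.

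**Direction.** Let R be the share of patients with a visit-documented CR/PR, l the share of those whose final entry is lower than CR/PR, and g the share of the remaining patients whose final entry is a CR/PR that no visit shows. With all final forms completed:

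reported rate = R(1 − l) + (1 − R)g

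The reported rate equals R when g = R·l/(1 − R). None of R, l or g is in the documents. Taking R = 30% purely as an assumption:

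| Assumed l | Reported rate if g = 0 | g at which the net change is zero |
|---|---|---|
| 10% | 0.30 × 0.90 = 27% | 0.03/0.70 = 4.3% |
| 25% | 0.30 × 0.75 = 22.5% | 0.075/0.70 = 10.7% |
| 50% | 0.30 × 0.50 = 15% | 0.15/0.70 = 21.4% |

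Above the value of g in the last column the reported rate is too high relative to the visits; below it, too low. Even the sign depends on quantities that the documents do not give. The table shows only that both directions are possible; it does not estimate a bias.

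**The case against.** The strongest reply is that the final item is probably a dedicated best-response field. A1.3 refers to best response by name and says what to do when it is missing. The flow charts describe the completion item as a global or overall rating, distinct from the visit rating. Table 2.1-2 lists reasons why best response was not assessable, and Table 2.1-3 reports the diagnostic technique for best response. All of this fits a field in which the physician records the best result over the whole course. On that reading, case b requires a mistaken entry. The physician's judgement is also the protocol's chosen response criterion, and a response seen between the last visit and completion may appear only on the final form.

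Most of this stands, and it rules out several stronger readings that a reader might infer:

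- **That the final entry is the status at discontinuation and so overwrites responses systematically.** No text describes it that way.
- **That response rates are biased downwards.** The rule can err either way, and no frequency is given.
- **That no imaging lies behind the final entry.** The flow charts do not mark imaging at completion, but Table 2.1-3 includes techniques that appear in neither protocol chart, so the charts are not a full list of CRF items.
- **That the two sources are never compared.** This is true of the SAP text. However, Protocol section 8 refers to a data validation plan with plausibility checks and queries, and its content is not available.
- **That the MCL survival analyses by response group are affected.** Tables 2.2-2 and 2.3-2 do not say which response variable defines the groups.

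The objection does not remove the gap. Even for a field meant as best response, the SAP lets a summary entry prevail over contradicting visit records and gives no way to resolve or report the conflict.

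**Conclusion.** The point holds as a gap in the derivation rule. A1.3 gives the final form unconditional precedence and has no provision for disagreement. It can therefore return a maximum response below a documented CR or PR, or one that no visit supports. How often this happens, and the net effect on the response rate, cannot be determined from the documents.

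The conclusion assumes that some final entries disagree with the visits and that no check outside the SAP resolves them all. The CRF and the data validation plan would settle how much of this is real. The consequence is limited to descriptive results: SAP sections 4.1 and 4.2 set no hypotheses or decision rules, so no error rate or sample size is involved. It is still worth correcting, because the endpoint is named in the objectives and the data needed are already collected.

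**What to change.** Amend SAP A1.3 and Table 2.1-2 as follows:

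1. State that best response is the best category over the whole documented therapy up to progression.
2. Where the final-form value and the best visit assessment disagree, raise a query. If it stays unresolved, use the better of the two, so that the final form cannot lower a visit-documented response. Do not restrict the final form to patients without any visit assessment, since that would discard a genuine response first recorded at completion.
3. Count the discordant cases in each direction in Table 2.1-2, including a final-form CR or PR that no visit supports.
4. Where the confirmed/not-confirmed split applies, derive it for CR and PR from the visit dates, using the interval of at least four weeks in Protocol section 11.

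The cost is one rule, a little programming and some queries. The drawback is that a single optimistic entry now counts as a response. It would count as unconfirmed, and both the split and the discordance count would make it visible.

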The biometric evaluation of the patient data (including statistical analysis plan) takes place, appropriate to the design of a registry, in a purely descriptive manner, and will be performed by a Contract Research Organization (Winicker Norimed GmbH, Nuremberg). An annual interim analysis will be performed.

Definition of analysis set

All prospectively documented patients with a histologically confirmed diagnosis of renal cell carcinoma, MCL, and GIST will be included in the "safety population".

All patients to whom at least one of the following criteria apply will be included in the "efficacy population": Date of death, time of progression, physician's assessment of therapy response, or therapy assessment of efficacy and tolerability by the physician are available.

Retrospectively documented information will not be included in the analysis.

Analysis of Safety Criteria

The absolute and relative frequency of patients with adverse events will be shown in a tabular form, both globally and according to the system organ classes and the MedDRA "preferred terms". In addition, the absolute and relative frequency of therapy dropouts will be presented both overall and according to discontinuation reasons. Serious adverse events will be evaluated separately. Previous and concomitant therapies will also be tabulated.

Laboratory analysis and electrocardiogram results will be analyzed per visit. In addition, the physician will assess information on tolerability during therapy.

Analysis of Efficacy Criteria

The change in disease activity will be described using the following parameters:

[figure not shown]
- Assessment of response to therapy by the physician
- Physician's assessment of efficacy
- Overall survival (OS)
- Progression-free survival (PFS)
- Maximum Response

For the analysis in STAR-TOR, the duration of treatment is defined as the period between inclusion in the registry and occurrence of any of the events of either death or discontinuation of the documentation or termination of therapy.

The duration of treatment will be evaluated using methods from the field of "survival time analysis".

Other analysis parameters

Comorbidities will be coded in accordance with MedDRA and concomitant medications according to WHO-DD. Frequencies for appropriate coding levels will be presented. Evaluation of sequence and therapy regimens and quality of life (advanced RCC) will be performed.

Case number estimate

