8.1.2 Analysis Of Survival Data

OS, PFS and treatment duration will be analyzed using Kaplan-Meier plots. Median, 25% and 75% survival times with confidence intervals for OS and PFS will be presented. For stratification according to physician's prognosis and for risk groups according to Motzer score/MIPI/Fletcher risk table, log-rank tests will be performed.

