Treatment duration (weeks) = (date of death or date of drop-out or date of end of treatment with Torisel®/ Sutent® - date of first infusion within the registry + 1)/365.25 * 52.

Therapy line

for patients with mRCC:

- Splitted therapy (due to coding) was only counted as one therapy line.
- All medication with an identical start date was counted as one therapy line.
- Interferons, interleukins and immunochemotherapies were summarized as "cytokines".
- Ongoing treatment with the medication documented was not counted as line.
- Bisphosphonates and other supplementary treatment will not be considered. for patients with MCL:
 - Splitted therapy (due to coding) was only counted as one therapy line.
 - All medication with an identical start date was counted as one therapy line.
 - Rituximab maintenance therapy and stem cell transplantation, both connected with previous immunochemotherapy (ATC L01 Antineoplastic agents and L03 Immunostimulants), were not counted as line.

Rituximub were counted as maintenance therapy, if

- physician's comment contained free text / phrases like "Erhaltung", "Erhalt", "Maintenance" or
- (last therapy prior to Rituximab resulted in remission (CR, PR or MR) and
- Rituximab was started directly after the last therapy (at most one therapy free month was tolerable).)

FKSI-15

For calculation of the FKSI-15 score documented values for questions 1-6, 8,9, 11, 12 and 14 will be reversed by subtracting the documented value from 4. All original scores (for questions 7, 10, 13 and 15) and all reversed scores will be summed, multiplied by 15 and devided by the number of answered questions resulting in a score within a range from 0 to 60. The FKSI-15 score cannot be determined if more than 7 questions are not answered.

FKSI-DRS score will be calculated like the FKSI-15 score considering only questions 1, 3, 4, 5, 6, 8, 11, 12 and 14 (multiply by 9). FKSI-DRS cannot be determined if more than 4 questions are not answered.

The 4 domains of FKSI-15 will be calculated like the FKSI-15 score. The following tables shows domains and related questions, multiplyer and maximal number of unanswered questions in order to give a valid score.

Domain	Questions	Multiplyer	Maximal number of unanswered questions
Signs and symptoms	1, 2, 3, 4, 5, 6, 12, 13	8	4
Respiratory symptoms	8, 11	2	1
Quality of life	7, 10, 13, 15	4	2
Emotional symptom	9	1	0

EQ-5D (TTO)

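### Treatment duration has no visible censoring rule and the protocol counts a stop of documentation as an event, so Kaplan-Meier time on drug runs short wherever patients leave while still treated

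*SAP*

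**What the plan says.** - **Protocol, section 11, Analysis of Efficacy Criteria.** Treatment duration runs from entry to the registry to the "occurrence of any of the events of either death or discontinuation of the documentation or termination of therapy". The next sentence says it will be evaluated with survival-time methods.
- **SAP, Appendix 1, A1.3, Treatment.** The interval ends at "date of death or date of drop-out or date of end of treatment with" Torisel or Sutent, and starts at the "date of first infusion within the registry".
- **SAP 8.1.2.** "OS, PFS and treatment duration will be analyzed using Kaplan-Meier plots".
- **SAP, Appendix 1, A1.3, Survival.** For PFS, "in case no progression was documented, subject was censored with the latest available contact date / assessment date within study/within sequence". For OS, "in case no death was documented, subject was censored with the latest available contact date / assessment date within study". The visible text has no matching rule for treatment duration.
- **Protocol, section 11, reasons for closing the follow-up documentation.** One reason is "Patient lost to follow up due to patient request/withdrawal of patient informed consent". Another is a change or stop of therapy for intolerance or progression.
- **SAP 2.1** likewise separates the end of treatment from a stop of documentation for some other reason.

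**The concern.** A Kaplan-Meier analysis needs an end date and a status, event or censored, for each patient. For treatment duration only the end date is given. The one text that speaks to status, in the protocol, calls a stop of documentation an event and lists it separately from the end of therapy. A patient who withdraws consent while still taking the drug would then be analysed as having stopped the drug on that day. A patient still on treatment at one of the interim data cuts has neither an end date nor a status.

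The result affected is the duration-of-therapy table (1.6-1), which SAP section 5 repeats for seven mRCC treatment-sequence groups. If on-treatment drop-out differs between groups, their curves would differ for that reason alone.

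The formula has three further defects, whatever is decided on censoring:
- It gives no end date for Inlyta, although the disease-duration formula in the same appendix names all three drugs.
- It starts at an infusion, but protocol section 5.2 describes sunitinib and axitinib as oral.
- Its start differs from the protocol's, which is entry to the registry.

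**Working it through.** The documents state no treatment duration, drop-out rate or number of treatment endings, so there is no planned figure to reproduce. The check asks how far event coding moves the estimate, and when.

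**Inputs**
- Time scale: 6 and 12 months, taken as assumed true medians. Protocol section 6 gives 6, 12 and 6 months for temsirolimus, sunitinib and axitinib, but as average observation periods, not treatment durations.
- q, the share of all endings that are drop-outs still on drug: not in the documents; assumed 5% to 30%.

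**Model.** Let the true end of treatment (including death on treatment) have constant rate a, and on-treatment drop-out have independent constant rate d. Then q = d/(a + d). If both are coded as events, the Kaplan-Meier curve estimates exp(−(a + d)t), so

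median = ln 2/(a + d) = (ln 2/a) × a/(a + d) = true median × (1 − q).

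Every other quantile shrinks by the same factor, so the whole plotted curve is affected. For example, at q = 20%: 6 × 0.80 = 4.8 and 12 × 0.80 = 9.6.

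| q (assumed) | True 6: drop-out as event | True 6: censored (simulated) | True 12: drop-out as event | True 12: censored (simulated) |
|---|---|---|---|---|
| 5% | 5.7 | 5.98 | 11.4 | 12.02 |
| 10% | 5.4 | 6.02 | 10.8 | 11.96 |
| 20% | 4.8 | 6.00 | 9.6 | 12.01 |
| 30% | 4.2 | 6.01 | 8.4 | 12.00 |

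The simulations used 400,000 patients per scenario. The simulated event-coded medians agree with the formula (5.69, 5.41, 4.79, 4.20 and 11.41, 10.77, 9.60, 8.40). The shortfall is 0.3 to 1.8 months on 6, and 0.6 to 3.6 months on 12.

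**No-bias case.** Where documentation closes because therapy was changed or stopped, the ending belongs to a, not d. Then q = 0 and event coding is correct.

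**Informative drop-out.** Suppose instead that a random share q leaves at 95% of their true treatment time, just before they would have stopped.

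| q (assumed) | True 6: event | True 6: censored | True 12: event | True 12: censored |
|---|---|---|---|---|
| 10% | 5.95 | 6.62 | 11.93 | 13.30 |
| 20% | 5.95 | 7.47 | 11.86 | 14.90 |
| 30% | 5.87 | 8.47 | 11.81 | 17.05 |

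Here event coding is nearly right and censoring overstates the duration.

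**The case against.** The strongest reply is that the SAP formula fixes only an end date. A censored patient's interval would close at the same drop-out date, so the formula does not show that drop-outs are events. A reader might infer that the SAP itself makes that choice; it does not say so. The event reading rests on one word in the protocol, in a sentence defining a period, together with the SAP's silence. The shell of Table 1.6-1 also falls in a blacked-out stretch of SAP section 9 and might state a rule.

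These points limit certainty but do not remove the problem. The protocol applies survival-time methods directly after that sentence, where event has a technical meaning. Nothing visible in the SAP overrides it, and the same appendix states censoring for PFS and OS.

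It can also be said that little depends on this variable. Treatment duration is not among the objectives (SAP 2.2), the endpoint tables (6.1, 6.2) or the summary of analyses (8.2.3). There are no hypotheses or decision rules. SAP 8.1.2 promises medians for OS and PFS, but only plots for treatment duration. Table 1.1-4 will show the reasons for premature discontinuation. All of this stands, and it keeps the point to a descriptive result.

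Finally, censoring is not automatically unbiased. Protocol 9.2 lets the physician end participation for safety or compliance reasons, so drop-out linked to an imminent stop is plausible. This also stands, and it is why the fix needs a sensitivity analysis.

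**Conclusion.** The point holds in a limited form. Followed as written, the Kaplan-Meier estimate of time on drug is biased short wherever patients leave documentation while still on treatment. The documents do not allow the size to be calculated. The illustration, a 5% to 30% shortening, rests on assumed drop-out shares, constant hazards and independent drop-out.

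Three stronger readings are tempting, but the documents do not support them:
- **Duration is biased for every drug.** That would need on-treatment drop-out in each group, and no rates are given. For axitinib the formula has no end date at all.
- **Closing the registry counts as an end of treatment.** Neither document lists it. What is missing is a status for treatment ongoing at a data cut.
- **Planned comparisons of duration between drugs or over calendar time are distorted.** The protocol plans to compare safety and efficacy between the drugs without naming treatment duration, and no calendar-time analysis of it appears.

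The missing Inlyta end date, the infusion start for oral drugs and the conflicting start dates are plain on the page and need no assumption.

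**What to change.** Use one definition in both documents:
- **Events:** permanent end of the documented drug, or death on treatment.
- **Censored at the last date known on treatment:** withdrawn consent, loss to follow-up, any other stop of documentation, and treatment ongoing at a data cut.
- **Sensitivity analysis:** repeat the analysis with drop-outs counted as events, and show the reasons for drop-out beside it.
- **Formula:** add Inlyta to the end date, replace the infusion start with the first registry dose of the documented drug, and reconcile that start with the protocol's.

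The cost is wording in two documents, one event flag and one extra Kaplan-Meier run. Reasons for discontinuation are already due to be tabulated. The small downside is that the main estimate will err long if drop-out tends to come just before a true stop; the sensitivity analysis shows how much this could matter.
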